Real world applicability of a study is enhanced if exclusion criteria are kept to a minimum. However, clear confounds should be avoided. Miller, et al., found that in young surgical patients, diabetes, cancer, kidney disease, hypertension, and abnormal BMI all significantly increased the chances of wound complications, while COPD, smoking, age, and HIV status did not.⁸² Yang, et al., found that smoking, hypertension, age, diabetes, and obesity did not delay VLU healing, and that males were more likely to have delayed VLU healing.⁸³ In contrast, Lane, et al., found that smoking dramatically reduced pressure injury healing, and McDaniel and Browning found that smoking negatively impacts chronic wound healing by impairing neutrophil function and fibroblast activity; decreasing both white and red blood cell production; increasing carbon monoxide, hydrogen cyanide, and other toxic compounds; causing tissue hypoxia; and causing the release of catecholamines.^{84,85} Smoking cessation programs led to improved wound healing.^{84,85} Parker, et al., found that delayed venous ulcer healing was correlated with living alone, ulcer duration > 24 weeks, and age > 70 years.⁸⁶ A review of studies of venous leg ulcer management demonstrated that 12 weeks were sufficient to determine if a treatment was effective or not.⁸⁷

2. Research Questions/Aim:

This study's primary purpose is to determine if an *improvised dressing*, made from inexpensive materials available for purchase in rural as well as urban settings, is a safe and effective, culturally and medically acceptable choice for managing sickle cell leg ulcers in a tropical climate. Three research questions will be addressed:

(1) Is the *improvised dressing*, consisting of a cut-to-fit new plastic bag sealed at the periwound with zinc oxide paste, safe and effective (see definitions, below) when compared with usual practice (saline-soaked gauze) and when compared with an advanced wound dressing (PMD), on sickle cell leg ulcers (SCLUs) in Jamaica?

(2) Does use of the *improvised dressing*, when compared with usual practice, improve the quality of life of patients (decrease pain, increase ability to engage in desirable activities, decrease wound-related materials costs, decrease time required to perform dressing changes, improve Wound QoL scores, and improve ASCQ-Me pencil-and-paper interview scores) with SCLUs in Jamaica?

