Decrease in SCLU surface area will be used to answer research question 1. Conducting a power analysis for this study is challenging because only one study of SCLUs has demonstrated a statistically significant outcome, and the effect size was obscured by high standard deviations, which is a common problem in studies of wounds.⁸ Improvised plastic dressings similar to the study dressings were used in 49 chronic pressure ulcers in elderly patients, which are often slow to close, if they heal at all.⁶⁰ These two studies demonstrated a significant difference with confidence intervals of 99% with ~25 patients per group. Based upon these sample sizes and the Central Limit Theorem, it is reasonable to set the minimum sample size for this study at 30 patients per group,.^{88,89}

d. Variables

Dependent Variables (measured weekly - tools and permissions in appendices):

- 1. Persistent wound pain (using the Faces Pain Scale Revised (FPS-R))
- 2. Procedural (dressing change) wound pain
- 3. Amount of pain medication taken, including a total number of morphine equivalents plus non-opioid pain medications
- 4. Approximate time spent standing, or sitting with leg dependent without compression (estimated hours per week)
- 5. Patient overall quality of life (assessed with the ASCQ-Me Emotional, Pain, Social Functioning, Stiffness, and Sleep Impact Short Forms)
- 6. Patient wound-specific quality of life (assessed with the Wound QoL tool)
- 7. Materials costs (estimated, using lowest retail costs on Amazon.com for items not on the UWI price sheets)
- 8. Time spent performing dressing changes
- 9. Wound complication rates (e.g., wound infection, healing impairing maceration, wound deterioration)
- 10. Change in wound surface area (measured in cm² electronically using software that automatically corrects for skew, such as HealthEPix or WoundMatrix)⁹⁰

Dependent Variables (measured one time, at graduation from study)

- 11. Wound closure time, in weeks (see definitions; verified two weeks later. Omit patients whose wounds did not fully close they are included in 10., above.)
- 12. Acceptability of dressing choice patient (5 point Likert scale and qualitative free response)
- 13. Acceptability of dressing choice family member (5 point Likert scale and qualitative free response)
- 14. Acceptability of dressing choice UHWI staff (5 point Likert scale and qualitative free response)

Independent Variables (documented at initial study visit):

1. Patient gender

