- 2. Age of open wound prior to entrance into study (in weeks, patient/family report)
- 3. Previous ulcer treatments (if any)
- 4. Education level (in years)
- 5. Smoking or any use of nicotine (yes/no in past week)^{84,85}
- 6. Mid-arm circumference (a surrogate for nutritional status) 91,92
- 7. Initial area of SCLU in cm^2 (see methods for multiple adjacent SCLUs)
- 8. Initial depth of SCLU at deepest point, in cm
- 9. Anatomic location of SCLU
- 10. ASCQ-Me baseline scores (all measures see appendices)
- 11. Social isolation (lives alone, without nearby support)⁸⁶
- e. Inclusion and exclusion criteria

Inclusion Criteria:

- > Diagnosed with HbSS or HbS β^0 sickle cell disease
- > Ages 13 70 years at study initiation (able to comprehend and give consent)⁸²
- > Males and females, pregnancy is not an issue
- > Open wound below the knee, not including the plantar surface of the foot
- > Wound open for longer than one month (defined as a chronic SCLU)
- > Traumatic, spontaneous, or recurrent SCLU (all etiologies)

Exclusion Criteria:

- > Patient younger than 13 years of age at study initiation
- > Patient older than 70 years of age at study initiation
- Wound open for less than one month by conclusion of study enrollment period (acute wounds could be traumatic wounds unrelated to sickle cell diagnosis)
- ➤ Diagnosis of cancer, hypertension, or chronic renal failure⁸²
- ➤ Diabetes (will screen for undiagnosed diabetes)⁸²
- Active wound infection (evidenced by clinical signs of malodor, dark-colored or thick drainage, or significantly increased warmth at the periwound) which is not resolved by the conclusion of the study enrollment period
- Osteomyelitis (if osteomyelitis is suspected, an ESR will be drawn; > 70mm/h with high platelet levels and low serum albumin warrants a bone biopsy)^{93,94}

> Hydroxyurea use (may be a confound because it reduces inflammation and negates much of the pathology of SSD – may choose to abstain for the study)^{7,95}

f. Sampling

- i. All eligible participants who consent to the study will be included. Participants will be randomized into one of the three groups immediately after the initial cleansing/debridement of their SCLU by the nurse using an electronic random number generator (an app). Waiting until the study dressing is to be applied to generate the random number will provide allocation concealment.

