Patients (and adult relatives of eligible patients under the age of 18) will have the study explained to them by one of the members of the UHWI surgical team. Questions will be addressed thoroughly. Families will be assured that if they choose not to participate in the study, the SCLU will be managed with usual practice. The patient (and a decision-maker of the family, in the case of a minor) must sign the consent for the patient to be enrolled in the study.

Immediately after consent is obtained, the study tools (Patient Data Collection sheet, Faces Pain Scale – Revised (FPS-R), ASCQ-Me, and Wound QoL) will be explained to the patient and family. Baseline persistent pain will be assessed using the Faces Pain Scale – Revised (FPS-R).

All of the initial independent variable data will be handwritten onto the patient's individual Study Data Collection Form upon enrollment in the study. The largest SCLU upon initial presentation is the study wound. All SCLUs will be measured for the first four weekly visits to UHWI. If two or more SCLUs in close proximity join during the first four weeks, the sum of the initial areas will be the initial wound size.

The SCLU(s) will be measured initially by placing two pieces of clear plastic on top of one another and tracing the wound edges. The plastic that came in contact with the wound(s) will be discarded and the plastic with the markings on it will be added to the patient's documentation so that the patient can be shown if the SCLU is becoming smaller at subsequent dressing changes. SCLU area will be measured in cm² electronically from a photo, using software such as HealthEPix or WoundMatrix.

Patients (with the support of their families) will be taught to evaluate and document persistent and dressing change pain, pain medication doses taken, time spent and supplies used at dressing changes, their activity, and their use of compression on a checklist-style Study Continuation Form daily. They will either provide the research team with their weekly summary and wound photo via WhatsApp, or they will attend the clinic weekly so that the research team can obtain this data. Two encrypted USB drives containing the data, including wound photographs, will be updated weekly on an alternating schedule and stored in a securely locked file in the UHWI surgical clinic dressing area, along with the paper study documentation.

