Study patients will be randomized into groups 1, 2, or 3 immediately AFTER initial thorough wound cleansing/debriding by the nurse or physician. Randomization will be accomplished using an electronic random number generator (an app).

After a member of the UHWI surgical team performs the initial cleansing/debriding, the control group (1) will have their ulcer dressed as usually done at UHWI. Wounds are dressed with saline-soaked gauze, covered with dry gauze. One wrap of stretch gauze will hold the dressing in place. Patients will clean the wound by vigorously wiping with gauze soaked in homemade normal saline (1 tsp salt/500ml water bottle), center to edges, at each dressing change, unless already very clean. Clean wounds will simply be irrigated with normal saline at each dressing change. Patients experienced with using papaya for debridement of their ulcers may apply it only to the open wound, avoiding contact with the periwound, to remove slough or eschar. If patients observe green exudate, they are permitted to add one teaspoon of vinegar to their bottle of saline. Dressings in group (1) will be changed daily. The dressings will be soaked off if they become adherent.

After initial cleansing/debriding, patients in the improvised dressing group (2) will then have a thin layer zinc oxide paste applied to the dried periwound, carefully avoiding the open wound.⁹⁷ A piece of a clean new plastic bag (food-grade World Star 1 mil LD bags, or the equivalent, purchased from the Papine Market across John Golding Road from the University of the West Indies), cut slightly larger than the ulcer will be gently conformed to the moist wound contours and sealed onto the zinc oxide paste. The bag will be fenestrated with a small slit using a number 11 scalpel or clean scissors prior to placing it on the ulcer in order to allow excess fluid to escape. The edges of the slit will be approximated. Clean gauze will be placed lightly over the slit to capture escaping fluid. One wrap of stretch gauze will hold the dressing in place. Patients will be instructed to change the dressings daily, irrigating with normal saline at each dressing change.⁶

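### Wound QoL and dressing-change pain have no specified pre-randomisation value, so their question 2 analyses lose precision and any check of starting balance

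*Combined protocol and SAP*

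**What the plan says.** Section 2 asks in question 2 whether the improvised dressing will, "when compared with usual practice, improve the quality of life of patients (decrease pain", and the same list goes on to "improve Wound QoL scores, and improve ASCQ-Me pencil-and-paper interview scores".

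Section 3d makes "Procedural (dressing change) wound pain" dependent variable 2 and "Patient wound-specific quality of life (assessed with the Wound QoL tool") dependent variable 6. Both are weekly measures, with no week 0 mentioned. The 11 independent variables, taken at the initial visit, contain one questionnaire score: "ASCQ-Me baseline scores (all measures see appendices"). They contain no Wound QoL score and no separate pain score.

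Section 3h covers the enrolment visit. Of the tools it says: "ASCQ-Me, and Wound QoL) will be explained to the patient and family. Baseline persistent pain will be assessed". That baseline is a Faces Pain Scale – Revised (FPS-R) rating of persistent pain. Patients are then randomised "immediately AFTER initial thorough wound cleansing/debriding by the nurse or physician".

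Section 3i analyses questions 1 and 2 by ANCOVA, with the independent variables as covariates. If superiority is not shown, sections 3a and 3i remove drop-outs and assess noninferiority in those who completed their allocated treatment.

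**The concern.** An outcome's own starting value is likely to be its strongest covariate. The authors named baselines for ASCQ-Me, persistent pain and ulcer area, so the silence on Wound QoL and dressing-change pain is a gap in the text. As written, the ANCOVA has no own-baseline term for either outcome. For persistent pain the value is collected and then left out of the covariate list.

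The first weekly score cannot safely stand in. By then the allocated dressing is in use, and section 5 accepts that participants cannot be blinded.

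Three things are at stake: the precision of the group comparison, the ability to describe within-patient change, and a check that groups of about 30 began at similar levels. The last matters more in the completers-only noninferiority analysis, where randomisation no longer guarantees balance. A baseline not taken before randomisation cannot be recovered later.

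**Working it through.** **Inputs from the documents.** About 30 per group, 90 in all, with up to 120 recruited for 25% dropout (3c, 3f). The 95% confidence intervals in 3i imply two-sided 0.05.

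**Inputs assumed.** Power of 80%, and a correlation r between baseline and follow-up of 0.3 to 0.7. The documents give no power, effect size, SD or correlation.

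**The plan's own figure.** 90 / (1 − 0.25) = 120, which matches. The 30 per group cannot be reproduced: 3c rests it on earlier sample sizes and the Central Limit Theorem.

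**Detectable difference without an own baseline.** The normal approximation gives (1.960 + 0.842) × √(2/30) = 0.72 SD. The t-based value is 0.736 SD and is used below.

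**With an own baseline.** Residual variance is multiplied by 1 − r², so the detectable difference is 0.736 × √(1 − r²). The group size that would match 30 without the baseline is 30 / (1 − r²).

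| r | 1 − r² | Detectable difference (SD) | Matching group size | Extra patients |
|---|---|---|---|---|
| none | 1 | 0.74 | 30 | – |
| 0.3 | 0.91 | 0.70 | 33 | 10% |
| 0.5 | 0.75 | 0.64 | 40 | 33% |
| 0.6 | 0.64 | 0.59 | 47 | 56% |
| 0.7 | 0.51 | 0.53 | 59 | 96% |

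For an assumed true effect of 0.5 SD, power (normal approximation) is 49% without an own baseline. With one it is 53%, 61%, 68% and 77% at r = 0.3, 0.5, 0.6 and 0.7.

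**Allowing for covariates already planned.** Suppose a listed variable such as baseline ASCQ-Me correlates 0.3 to 0.4 with the outcome (assumed). Power for 0.5 SD is then already 53% to 56%. Replacing a proxy at 0.3 with an own baseline at 0.5 gives a variance ratio of 0.75 / 0.91 = 0.82. Replacing 0.4 with 0.7 gives 0.51 / 0.84 = 0.61. The extra-patient equivalents are 1/0.82 − 1, about 21%, and 1/0.61 − 1, about 65%.

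**Does the omission bias the comparison?** In 10,000 simulated trials with 30 per group, complete data and r = 0.6, rejection under no effect was 4.9% unadjusted and 5.0% adjusted. With a true 0.5 SD effect both estimates averaged 0.50 SD, and power was 48% unadjusted and 65% adjusted. The loss is of precision only. The simulation does not cover the completers-only analysis.

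**The case against.** The strongest reply is that question 2 compares randomised groups, and that contrast needs no baseline. This stands. A reader might infer that improvement cannot be measured at all, but the question is framed against usual practice and the simulation shows no bias. Chance imbalance is already reflected in the confidence interval.

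Second, the text is silent rather than explicit. A reader might infer that both scores are first recorded after randomisation, by patients who know their dressing. No sentence says so. The collection forms are in appendices not available here, and 3h does not say whether the enrolment day counts as a weekly assessment. Nor does the word for explaining the tools show that Wound QoL was left blank: the same sentence covers ASCQ-Me and FPS-R, which do have baselines. The firmer evidence is its absence from the list in 3d. The point is therefore that these baselines are not specified in the protocol text.

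Third, the ANCOVA already includes baseline ASCQ-Me (which has a pain form), ulcer area, depth and duration. This also stands and reduces the gain, as shown above.

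Fourth, the initial cleansing/debriding might look like a ready-made baseline for procedural pain. It is done by a clinician, the text does not say it is uniform across patients, and it differs from the dressing changes patients later rate. It is a weak proxy.

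Finally, question 1 is unaffected, because initial ulcer area is recorded and is a covariate.

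**Conclusion.** The point holds as a cheap gain in efficiency, not as a flaw that invalidates question 2. The protocol text specifies no pre-randomisation Wound QoL or dressing-change pain score and adjusts neither outcome for its own baseline. Baseline persistent pain is collected but not listed as a covariate.

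At 30 per group the detectable difference could fall from about 0.74 SD to between 0.70 and 0.53 SD. This rests on an assumed correlation of 0.3 to 0.7 and on a comparison with no other covariate; the real gain is smaller to the extent that ASCQ-Me and wound size already explain variance. At the low end it is slight. Since the sample size rests on no stated effect or SD, the plan shows no spare power.

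Under full intention to treat the comparison is unbiased. In the completers-only analysis, the missing baselines mean that neither balance nor differences between completers and drop-outs can be checked on these scores.

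**What to change.** In 3h, state that after consent and before the random number is drawn the patient:

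- completes Wound QoL in the same sitting as ASCQ-Me; and
- gives one FPS-R rating of usual pain at dressing changes before the study. A rating of the initial cleansing/debriding may be added, but only as a weaker proxy.

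In 3d, add both scores and the already collected baseline persistent pain to the independent variables, making 11 + 3 = 14. In 3i, update the count and state that each is the covariate in the ANCOVA for its own outcome. If the appendix forms already provide for a Wound QoL entry at enrolment, the change for that score is only to say so and to use it.

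Pain medication, dressing-change time and materials cost also have no stated starting value; the sponsor should say whether one is intended.

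The cost is a few minutes per patient at a visit already planned, plus some recall error in the pain rating. No treatment or visit changes.

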- Based upon previous studies and the Central Limit Theorem, an estimated 90 participants (~30 per group) may be required for the differences between groups to reach statistical significance.^{12,23,88,89,96} Up to 120 patients will be recruited to allow for a 25% dropout rate. Based upon the literature review, pain, costs, wound size, and quality of life are expected to be significantly improved using the improvised dressings. However, because SCLUs are, historically, very slow to heal and often enlarge, complete wound closure is not an expected outcome for all patients.

g. Procedures for recruitment and consent

The study will be advertised using free community information channels such as church bulletins and radio outlets. Social media sites such as the CAIHR Facebook page will also be employed. Qualifying patients in the SCU database from up to two years prior to the study initiation will be called by the UHWI surgical team, alerting them to the dates for registering to participate. Flyers will be posted at the SCU in advance. Consent will be obtained by a member of the research team while the potential participant is waiting to be seen for wound care.

h. Data collection

The site for this study is the surgical clinic dressing area at the University Hospital of the West Indies (UHWI), Mona, Jamaica. The adjacent Sickle Cell Unit (SCU) will refer any SCLU patients to UHWI during the study period. UHWI is consistently well staffed with competent Jamaican health professionals. The UHWI surgical team will lead the study. Relatively few Jamaicans live or work in air-conditioned environments, ^[data in appendices] allowing the results from this out-patient population to translate to less developed tropical countries.

To ensure consistency, members of the research team will practice until they can demonstrate competency with all three dressing change procedures and with explaining the study forms prior to study patient recruitment.

Enrollment in the study will begin within two weeks of the day the Principal Investigator arrives at the Mona campus and will close 60 days later, or when a maximum of 120 patients have enrolled. All sickle cell positive patients presenting to UHWI with lower leg ulcers during the enrollment period will be screened for eligibility to enter the study. Each patient's data will be recorded for a total of 12 weeks, or until their SCLU has been closed for 2 weeks, whichever comes first.

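### Baseline FPS-R wound pain is collected before randomization but is missing from the 11 covariates of the ANCOVA that tests persistent wound pain

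*Combined protocol and SAP*

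**What the plan says.** All references are to the combined protocol and SAP.

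- **Outcome.** Section 3d lists, as dependent variable 1 measured weekly, "Persistent wound pain (using the Faces Pain Scale Revised (FPS-R"). Research question 2 (section 2) asks whether the improvised dressing improves quality of life, and its components begin "decrease pain, increase ability to engage in desirable activities, decrease wound-related materials costs". Section 3f adds that "pain, costs, wound size, and quality of life are expected to be significantly improved using the improvised dressings".
- **Baseline.** Section 3h, on the steps that follow consent: "Baseline persistent pain will be assessed using the Faces Pain Scale" – Revised.
- **Allocation.** Section 3h: "Study patients will be randomized into groups 1, 2, or 3 immediately AFTER initial thorough wound cleansing/debriding", and "Randomization will be accomplished using an electronic random number generator (an app"). Neither 3f nor 3h describes stratification or blocking.
- **Model.** Section 3i addresses questions 1 and 2 by ANCOVA for each dependent variable, adjusting for the independent variables, and gives their number as 11.
- **Covariates.** The list in 3d includes, as item 7, "Initial area of SCLU in cm^2 (see methods for multiple adjacent SCLUs") and, as item 10, "ASCQ-Me baseline scores (all measures"). Baseline FPS-R is not on it.

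**The concern.** An outcome's own baseline is usually the covariate that explains most of its follow-up variance. The plan follows this for ulcer area and for ASCQ-Me, but not for persistent wound pain, although that baseline is already collected. The nearest item on the list is the ASCQ-Me Pain form. It is a different instrument, used here for overall quality of life, so it is only a partial stand-in for wound pain.

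Allocation is random, so the omission causes no systematic bias. Two things are at stake: precision, in a trial of about 30 per group with no power calculation for pain, and protection against a chance difference in baseline pain, which nothing in the design balances. Question 1 rests on ulcer surface area and is not affected.

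**Working it through.** **1. List check.** The 11 independent variables are gender, age of wound, previous treatments, education, nicotine use, mid-arm circumference, initial area, initial depth, location, ASCQ-Me baseline scores and social isolation. That makes 11, and none is FPS-R. No section adds it elsewhere or defines pain as a change from baseline.

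| Outcome | Baseline collected | Baseline in covariate list |
|---|---|---|
| Persistent wound pain, FPS-R (dependent variable 1) | yes | no |
| ASCQ-Me (dependent variable 5) | yes | yes, item 10 |
| Ulcer area (dependent variable 10) | yes | yes, item 7 |

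**2. Timing.** Consent is taken while the patient waits for wound care (3g). The tools and baseline pain follow at once (3h). Cleansing and debridement come next, then randomization (3f, 3h). Baseline pain therefore precedes allocation. This is inferred from the sequence; no single sentence says it.

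**3. The plan's own figure.** 90/(1 − 0.25) = 120 reproduces the recruitment target. The 30 per group cannot be reproduced, because no effect size, SD or power is given.

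**4. Gain beyond one ASCQ-Me score.** Let A be baseline ASCQ-Me, B baseline FPS-R and Y follow-up FPS-R, with q = corr(A,B), r = corr(B,Y) and s = corr(A,Y). The documents give none of these; I take q from 0.3 to 0.7 and r as 0.3, 0.5 or 0.6. The further cut in residual variance from adding B is the squared partial correlation

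(r − qs)² / [(1 − q²)(1 − s²)].

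Two cases bound s: A predicts Y only through B (s = qr), or A predicts Y as well as B does (s = r). Example with r = 0.5, q = 0.3, s = 0.15: (0.5 − 0.045)² / (0.91 × 0.9775) = 0.207/0.890 = 0.233.

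| r | s = qr; q = 0.3, 0.7 | s = r; q = 0.3, 0.7 | Range |
|---|---|---|---|
| 0.3 | 0.083, 0.048 | 0.053, 0.017 | 2–8% |
| 0.5 | 0.233, 0.145 | 0.179, 0.059 | 6–23% |
| 0.6 | 0.339, 0.223 | 0.303, 0.099 | 10–34% |

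**5. Gain beyond the full covariate set.** Simulation of three arms of 30, 6,000 trials per setting, true difference 0.6 SD. The Pain form correlates q with B and the four other ASCQ-Me forms 0.5q. The forms intercorrelate 0.5. Ten further covariates each correlate 0.1 with B. In the s = r case the other forms correlate 0.5r with Y and the ten covariates 0.1 each.

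| r | Variance cut | Power, s = qr; q = 0.3, 0.7 | Power, s = r; q = 0.3, 0.7 |
|---|---|---|---|
| 0.3 | 0–7% | 0.569→0.594, 0.583→0.595 | 0.629→0.632, 0.639→0.633 |
| 0.5 | 1–21% | 0.565→0.665, 0.619→0.669 | 0.733→0.780, 0.742→0.740 |
| 0.6 | 3–31% | 0.583→0.743, 0.650→0.734 | 0.804→0.890, 0.811→0.814 |

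Under the null, rejection in the favourable direction was 0.022–0.027.

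**6. Dependence on the pain value used.** If pain is analysed as change from baseline without B as a covariate, the cut is 1 − Var(Y|A,B)/Var(Y − B|A): 22–39%, 15–36% and 11–37% for r = 0.3, 0.5 and 0.6. For the mean of 12 weekly scores (intercorrelation 0.6 assumed) it is 3–13% at r = 0.3 and 12–37% at r = 0.5.

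**7. Chance imbalance.** With 30 per group, the SE of the baseline difference is √(2/30) = 0.26 SD. Simulating simple randomization of 90 patients (400,000 draws), groups 1 and 2 differ by more than 0.5 SD in 5.6% of trials and by more than 0.3 SD in 25%. At least one of group 2's two comparisons exceeds 0.5 SD in 10.0%. With 120 patients analysed, the first two figures are 2.7% and 18%.

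After adjustment for one ASCQ-Me score, a 0.5 SD imbalance still moves the pain difference by 0.5r(1− q²) when s = qr, or by 0.5r(1 − q) when s = r. At r = 0.5 these are 0.228 and 0.128 (q = 0.3, 0.7), and 0.175 and 0.075. Overall the shift is 0.05–0.14, 0.08–0.23 and 0.09–0.27 SD for r = 0.3, 0.5 and 0.6.

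**The case against.** The strongest reply is that the effect may be small. Every correlation is assumed, and ASCQ-Me, including its Pain form, is already in the model. If that form tracks wound pain closely and predicts follow-up equally well, baseline FPS-R adds almost nothing; the largest gains need a weak proxy. This stands, and it is why the results are given as ranges that start near zero. It limits the size of the point but gives no reason to leave the covariate out.

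The imbalance risk also falls if all 120 recruited patients are analysed, as intention-to-treat might imply. The plan does not say how dropouts enter that analysis, so both sample sizes are shown. At a typical imbalance of one SE (0.26 SD), the shift after ASCQ-Me adjustment is only about 0.02–0.14 SD.

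Two limits of scope are fair. Only persistent pain has a described baseline, so the point does not carry over directly to procedural pain (dependent variable 2). Section 3i also names Student's t test and ANOVA, which a new ANCOVA covariate would not change; but ANCOVA is the method it assigns to question 2.

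Finally, pain is recorded weekly and the plan does not say which value is analysed. That is a gap in its own right, and step 6 shows that the benefit depends on it. It does not remove the omission.

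**Conclusion.** The point holds. By the plan's own list, the ANCOVA of persistent wound pain omits that outcome's pre-randomization baseline, while the baselines of area and ASCQ-Me are included. The cost is precision and exposure to chance imbalance in one component of question 2.

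The gain from adding baseline FPS-R is negligible if baseline and follow-up pain correlate weakly or the ASCQ-Me scores are good proxies. It is material if the correlation is 0.5 or more and the proxies are imperfect: at best a 21–31% cut in residual variance and 10–16 points of power at 30 per arm. The omission itself is certain from the text. Its size rests wholly on assumed correlations and an assumed 0.6 SD difference. The change is worth making, but its absence does not invalidate the trial.

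**What to change.** Add baseline FPS-R as a covariate in the ANCOVA of persistent wound pain. In the same SAP text, state before any outcome data are seen which pain value that model uses: one named visit, a change from baseline, or a stated summary of the weekly scores.

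The cost is a wording change and one degree of freedom; the data are already to be collected. In the least favourable setting simulated (r = 0.3, proxies as predictive as FPS-R, q = 0.7), power moved from 0.639 to 0.633, a loss of about 0.6 point.

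A minor wording matter, separate from this point, can be settled at the same time. The definition of effectiveness in section 2 speaks of rates of area reduction, while dependent variable 10 in 3d is a change in area measured in cm². One scale and one analysis visit should be named.
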